Randomisation was conducted using simple randomisation, within classes (or effectively within schools where there was only one reception class). As the number of schools recruited exceeded the delivery target, as per the trial protocol, in schools with multiple reception classes, only one class was selected (at random) to complete the pre-tests. This means that while a total of 2,646 pupils were in classes eligible for testing, a total of 3,662 pupils form part of the overall trial. Pupils in the classes that were not selected for testing were still randomised; the original intention being that outcomes from the Early Years Foundation Stage Profile (EYFSP) would be analysed as secondary outcomes for the full sample of 3,662 pupils. As documented in the protocol revisions (version 1.1), analysis of EYFSP outcomes is no longer possible, as in line with other national assessments, these assessments did not take place in summer 2020 due to the Covid-19 pandemic. While beyond the scope of the current planned analysis, this larger sample could potentially be followed up in future longitudinal analysis.

Due to a small number of schools having an earlier October half-term (2019), randomisation took place in two batches, enabling parents in these schools to start receiving the texts immediately following half-term. Five schools were randomised in the first batch (20th October 2019) and the remaining 104 schools in the second batch (30th October 2019).

Sample size calculations overview

		Protocol		Randomisation	
		OVERALL	FSM	OVERALL	FSM
Minimum Detectable Effect Size (MDES)		0.10	0.14	0.10	0.15
Pre-test/ post-	level 1 (pupil)	0.4	0.4	0.4	0.4
test correlations	level 2 (class)	-	-	-	-
	level 3 (school)	-	-	-	-
Intracluster correlations	level 2 (class)	-	-	-	-
(ICCs)	level 3 (school)	0.10	0.10	0.10	0.10
Alpha		0.05	0.05	0.05	0.05
Power		0.8	0.8	0.8	8.0
One-sided or two-sided?		2	2	2	2
Average cluster size		26	10	24	9
	intervention	105	105	109	109
Number of schools*	control	105	105	109	109
30110013	total	105	105	109	109
Number of pupils	intervention	1365	525	1325	510
	control	1365	525	1321	508
	total	2730	1050	2646	1018

^{*}Note that as randomisation took place within schools (classes), all schools form part of both the intervention and control group.

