The sample size was determined with the aim of establishing a MDES of 0.1, given the previous research by York and Loeb (2018), which found an impact of the programme on literacy of 0.11 standard deviations. MDES calculations were conducted using Optimal Design software.

All estimates are based on standard EEF assumptions of 80% power and 5% significance level. We assume the pre-test explains 40 per cent of the variation in the post-test scores¹, and that 10 per cent of variance is explained by the blocking variable² (or effectively here, an ICC of 0.10). To achieve an MDES of 0.1 this suggested a required sample size of around 105 schools based on an average of 26 pupils per school (assuming an average of 30 pupils per school, and then allowing for around 5 per cent of pupils to withdraw before randomisation and around 10 per cent of the remainder lost to follow-up). As set out in the trial protocol, if it proved feasible to recruit around 105 schools (and ultimately 109 were recruited), then only 1 class per school receives the assessment that forms the primary outcome for the trial.

Department for Education Statistics for January 2019 show that 15.8 per cent of pupils in primary schools were eligible for and claiming free school meals (Department for Education, 2019). However, schools with above average proportions of pupils eligible for free school meals (FSM) were targeted in recruitment. On the assumption that on average 10 pupils within the reception year of a school will be eligible for FSM, equivalent to around 38 per cent of pupils (at the time of writing the protocol, this was the average percentage of pupils eligible for FSM in recruited schools), and keeping all other assumptions the same, this results in an MDES of 0.14. The trial is not however designed with the aim of detecting an effect for the FSM subgroup as the primary population of interest.

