At the point of randomisation, 109 schools were recruited and 2,392 pupils had completed pre-tests. In total, 2,646 pupils were in the classes selected for the pre-test, and were randomised; all of these pupils will be approached for post-test.³ This means the maximum available sample at post-test is 2,646 (note this excludes 2 pupils who were withdrawn from the study after randomisation, based on the available information at the point of preparing this SAP). Based on these numbers, and keeping all other assumptions the same as at protocol stage, this gives an MDES of 0.10. There will inevitably be some degree of attrition from the trial by the point of analysis. If we assume that ultimately 100 schools remain in the trial, with an average cluster size of 20, the MDES stands at 0.11. For the FSM subgroup, based on post-randomisation numbers, the MDES stands at 0.15. Given the likely difficulties in conducting assessments as a result of Covid-19, it is probable that attrition will be higher; with attrition of around 20 per cent of schools, this would result in an MDES of 0.12. Thus even with fairly substantial attrition, the trial would still be able to detect a relatively small effect. To help place this in context, in line with EEF guidance, an effect size of between 0.10 and 0.18 is considered to be equivalent to two months' additional progress.

_

¹ To our knowledge, there is currently no publicly available information on the likely correlation between pre- and post-test scores for our primary outcome measure, the York Assessment of Reading for Comprehension. The efficacy trial of the Nuffield Early Language Intervention (implemented with a similar age group) found that around 55% of the variation in post-test scores (a composite language score) was explained by the pre-test and pupil characteristics (Sibieta, 2016). This would be higher due to the additional inclusion of pupil characteristics; we therefore use a lower estimate of 40 per cent for our assumption.

² As noted earlier, randomisation was conducted within schools, or blocks. The sample size calculations require an estimate of the percentage of the variance explained by the "blocking variable", in this case, the percentage of the variance explained by the school (Spybrook et al., 2011). Although based on secondary schools, previous research has indicated that schools explain around 10 per cent of the variation in pupil attainment at the end of Key Stage 4 (Wilkinson et al., 2018)

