We will conduct exploratory analysis that examines separately whether there is an impact of the intervention on each of the four YARC subscales administered at post-test: letter sound knowledge, early word recognition, sound isolation, and sound deletion. This will follow the same model specification for the primary outcome, and adjust for the total YARC pre-test score in each case.

Analyses in response to missing data are discussed further below.

Update v1.1: Due to the third national lockdown and associated disruption for schools as a result of Covid-19, the decision was taken to stop post-testing in January 2021. This has resulted in a smaller number of completed post-assessments (around a third of the anticipated number). The smaller than anticipated sample size available for analysis inevitably has implications for the ability of the originally proposed analysis to detect a statistically significant effect (more generally, there is of course wider debate around the use of p-values to judge statistical significance, see for example, the discussion in Nuzzo, 2014). Bayesian methods can be used as an alternative means of evaluating effectiveness and may, though not in all circumstances, offer benefits when working with smaller sample sizes (McNeish, 2016).

While we will carry out the original analysis using frequentist methods as documented in the original version of this SAP, we will also undertake an additional exploratory analysis using a Bayesian approach. This will provide exploratory evidence into the probability that the

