intervention has a positive effect. This additional analysis will be carried out for both primary and secondary outcomes, and will be estimated using the eefAnalytics package available within Stata (Vallis et al., 2021). For this analysis we will adopt non-informative priors; this is to ensure that the results are in large part driven by the data, rather than on a subjective judgement regarding priors (Uwimpuhwe et al., 2020). For consistency, we will adopt the same assumptions regarding non-informative priors as used in the analysis by Uwimpuhwe et al. (2020) which uses vague Gaussian priors (N(0,106) for each of the regression parameters. The report will present the effect sizes and credible intervals estimated through the Bayesian approach; along with the posterior probability that the intervention has an effect size of at least 0.1. This follows the recommendation made by Uwimpuhwe et al. (2020) regarding a suitable threshold for assessing effectiveness of educational interventions, but is also consistent with the fact that the trial was designed with the aim of establishing a MDES of 0.1, given the previous research for the US by York and Loeb (2018), which found an impact of the programme on literacy of 0.11 standard deviations. For completeness, we will also report the probability that the intervention has an effect size of at least zero (that is, that it has a positive effect). The results from the frequentist analysis will remain the main results on which the report will focus, with the results from the Bayesian approach forming an additional exploratory analysis, to provide further insight into the sensitivity of results. Any substantive differences in the results obtained from the two approaches will be discussed in the evaluation report.

Longitudinal follow-up analyses⁵

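### SAP v1.1 reports about a third of the anticipated post-tests but leaves the sample size section at an MDES of 0.10 to 0.12; the achieved sample implies about 0.14 to 0.19 overall

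*SAP*

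**What the plan says.** The sample size table in the SAP (Sample size calculations overview) has two stages, Protocol and Randomisation. The overall MDES is 0.10 at both, and the FSM MDES is 0.14 and then 0.15. The text adds two attrition scenarios: 0.11 for 100 schools with 20 pupils each, and "with attrition of around 20 per cent of schools, this would result in an MDES of 0.12". From these it concludes: "Thus even with fairly substantial attrition, the trial would still be able to detect a relatively small effect". It then cites EEF guidance that 0.10 to 0.18 corresponds to two months' additional progress.

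The v1.1 update under Additional analyses reports that post-testing stopped in January 2021, leaving completed assessments at "around a third of the anticipated number". It accepts that this affects the chance of a statistically significant result and adds an exploratory Bayesian analysis, while the frequentist results stay the main ones. It also recalls that "the trial was designed with the aim of establishing a MDES of 0.1". It gives no MDES or power for the achieved sample. The sample size section carries no revision and no pointer to the update.

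**The concern.** Both statements are current body text of v1.1; neither belongs to a log of superseded wording. The most pessimistic overall MDES that the SAP gives assumes that about a fifth of schools are lost, whereas the same document reports that about two thirds of the anticipated post-tests are missing. The conclusion that follows the 0.12 is therefore drawn from a scenario much milder than the one that occurred.

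The figure matters for interpretation. The trial was sized for 0.10 because an earlier study of the programme found 0.11. A reader who sets a non-significant main result beside a stated MDES of 0.10 to 0.12 could take it as evidence against an effect of that size, although power for such an effect is now far below 80%. The gap is wider for FSM pupils.

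**Working it through.** **Inputs (SAP, Sample size calculations overview)**
- "All estimates are based on standard EEF assumptions of 80% power and 5% significance level"; the table row "One-sided or two-sided" is answered 2. The multiplier is 1.960 + 0.842 = 2.80.
- "We assume the pre-test explains 40 per cent of the variation in the post-test scores", so R² = 0.40. The table lists the same 0.4 as a pre-test/post-test correlation, which would give R² = 0.16. Both are run.
- "10 per cent of variance is explained by the blocking variable", so B = 0.10.
- Allocation is 1:1 within class.
- The base for the third is not stated. Assumed: 2,000 (the 100 × 20 scenario), 2,646 (maximum available at post-test) or 2,730 (protocol total). One third is about 667, 882 or 910 pupils.

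**Formula** (individual randomisation within schools, school fixed effects)

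MDES = 2.80 × √[4(1 − R²)(1 − B)/N]. The numerator 4(1 − R²)(1 − B) is 2.16 for R² = 0.40 and 3.024 for R² = 0.16.

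**The SAP's own overall figures**

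| Case | N | Stated | R² = 0.40 | R² = 0.16 |
|---|---|---|---|---|
| Protocol | 2,730 | 0.10 | 0.079 | 0.093 |
| Randomised | 2,646 | 0.10 | 0.080 | 0.095 |
| 100 × 20 | 2,000 | 0.11 | 0.092 | 0.109 |
| 20% of schools lost, 87 × 20 | 1,740 | 0.12 | 0.099 | 0.117 |
| 20% of schools lost, 80 × 20 | 1,600 | 0.12 | 0.103 | 0.122 |

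Pupils per school in the 20% scenario are not stated. With 87 × 24 = 2,088 the results are 0.090 and 0.107. R² = 0.40 gives values below every stated figure. R² = 0.16 comes close to the 0.11 and 0.12, but gives 0.150 for the protocol FSM case (N = 1,050), where 0.14 is stated. Neither reading reproduces the whole set.

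All six stated values are matched to two decimals by adding a between-school variance of the treatment effect of 0.05, with R² = 0.40 and t multipliers on J − 1 degrees of freedom: MDES = (t₀.₉₇₅ + t₀.₈₀) × √[(0.05 + 2.16/n)/J], for J schools with n pupils each and 87 × 20 for the 20% scenario. The SAP does not state that 0.05; it was fitted here and is only a sensitivity check.

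**Achieved sample, overall**

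| N | R² = 0.40 | R² = 0.16 |
|---|---|---|
| 667 | 2.80 × √(2.16/667) = 0.159 | 2.80 × √(3.024/667) = 0.189 |
| 882 | 0.139 | 0.164 |
| 910 | 0.136 | 0.162 |

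Two cross-checks agree in direction. Scaling the SAP's 0.10 and 0.11 by √3 gives 0.17 and 0.19. The fitted-variance basis gives 0.153 (109 schools × 8) to 0.180 (36 schools × 24).

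**Power, N = 667 to 910**

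The standard error is √(2.16/N) or √(3.024/N). At N = 667 and R² = 0.40 it is 0.0569; 0.10/0.0569 = 1.76, and Φ(1.76 − 1.96) = 0.42.

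| True effect | R² = 0.40 | R² = 0.16 |
|---|---|---|
| 0.10 | 42 to 54% | 32 to 41% |
| 0.11 | 49 to 62% | 37 to 48% |
| 0.12 | 56 to 69% | 43 to 55% |

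An MDES of 0.12 needs N = 2.16 × (2.80/0.12)², about 1,180 pupils, or about 1,650 with R² = 0.16.

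**FSM pupils**

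The share at randomisation is 1,018/2,646 = 38.5%. If it is unchanged among tested pupils, N is about 257 to 350. The MDES is 0.22 to 0.26 (R² = 0.40) or 0.26 to 0.30 (R² = 0.16), against a stated 0.15.

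**The case against.** The shortfall is not hidden. The version history gives it as the reason for v1.1, and the update says plainly that detecting a significant effect becomes harder. The sample size text is conditional and written before the shortfall. Its table columns are labelled by stage, so later attrition does not make the 0.10 and 0.15 wrong as Protocol and Randomisation figures. The recollection that the trial was designed for 0.10 also remains true. All of this stands.

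Three stronger readings are tempting, and the SAP does not support them. A reader might infer that 0.12 was offered as a worst case. The SAP presents it only as the result of losing about 20% of schools, although it is the largest overall MDES given. A reader might also infer that the concluding sentence is simply false. The SAP does not define a relatively small effect, and the next sentence cites a band of 0.10 to 0.18, which contains most of the recomputed range. The sentence fails clearly for effects of 0.10 to 0.12, and only arguably beyond that. Finally, a reader might infer that the SAP would treat a non-significant result as no effect. It contains no such rule. It plans 95% confidence intervals around effect sizes and posterior probabilities of an effect of at least 0.1 and at least zero. It also says the trial was not designed around the FSM subgroup.

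These points limit the finding but do not remove it. The warning in the update carries no number, and the section where a reader looks for the MDES still stops at 0.12.

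**Conclusion.** The point holds as a failure to update a stated sensitivity figure. No variant run brings the achieved overall MDES to 0.12 or below: it is about 0.14 to 0.16 with R² = 0.40 and 0.16 to 0.19 with R² = 0.16. Power for the design effect of 0.10 is roughly 32 to 54%. The FSM MDES is about 0.22 to 0.30.

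The exact values rest on an assumed base of 2,000 to 2,730 for the anticipated number, on which meaning of 0.4 applies, and, for FSM, on an unchanged share among those tested. The direction depends on none of the first two, since about 1,180 pupils at the least are needed for 0.12 and at most about 910 are available under these assumptions. The failure of the stated inputs to reproduce the stated MDES values is a separate matter and does not alter this conclusion. No model, estimand or decision rule is affected.

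**What to change.** In the sample size section:
- Keep the Protocol and Randomisation figures and the two attrition scenarios, marked as pre-shortfall.
- Add an Analysis column with the actual numbers of schools, pupils and FSM pupils that have post-tests, and the MDES recomputed from them.
- Qualify the concluding sentence with a cross-reference to the v1.1 update, saying that it no longer holds for effects of 0.10 to 0.12.

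The ranges given here should not be copied into the SAP; they stand in for counts that the evaluators hold. A rule for reading a non-significant result by whether the confidence interval excludes 0.10 would be a reporting preference, and this correction does not need it.

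The cost is a change of wording and one table column. The downside is that the stated sensitivity becomes less favourable.

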³ Except in the event of further withdrawals. Pupils who have subsequently left their school will also not be tested.

Analysis

The estimated impact will be based on the difference between those assigned to the treatment and control groups, regardless of contamination of the control group or drop out. This is in order to estimate the "intention-to-treat" (ITT) effect. In addition, the regression models used for the primary analysis will include controls for prior attainment (that is, using the YARC total score as captured at pre-test), as well as a dummy variable to indicate those schools which were randomised in the first batch.

Estimated impact in terms of pupil's outcomes will be converted into a Hedges' g effect size. This will use the estimated total pooled standard deviation of the treatment and control groups, rather than the within-school pooled standard deviation as the former is a more conservative approach.

For each measure, we will estimate outcomes using a linear regression model including a dummy variable indicating trial arm allocation, and school fixed effects. We prefer this approach over multi-level analysis which relies on an assumption that random effects are independent of regressors (Ebbes, 2004).

Primary outcome analysis

The primary outcome to be assessed in this trial is literacy, as measured by the York Assessment of Reading for Comprehension (YARC). The version of the YARC suitable for 4-7 year olds is called Early Reading and covers four dimensions: sound isolation, sound deletion, letter sound knowledge, and early word recognition. To reduce testing time and burden on the school, only the former two measures were used as a pre-test as they are considered the most sensitive and more appropriate for the younger age of the children by GL Assessment and then all four dimensions are to be used at post-test. The primary outcome will be a "total" YARC score, where we will standardise each of the components to have a mean of zero and standard deviation of one. These will then be added together to create a composite measure and re-standardised (calculated where all four components are non-missing). We propose this approach, rather than simply summing together the four scales, given the subscales are not of equal length and thus a simple sum would give greater weight to the longer subscales. The same approach will be adopted with the two subscales used for the pre-test.

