More precisely, our outcome measure will be the total difficulties score from the SDQ. This is a standard SDQ measure which is constructed from summing together responses on four of the five SDQ subscales, giving a score which ranges from 0 to 40. Following existing conventions in using the SDQ (Vaz et al., 2016), if at least three of the five items within a subscale are completed, any remaining missing scores will be replaced by the mean for that subscale. If fewer than three items are completed, no score will be computed for that subscale, and if any of the four subscales are missing, the total difficulties score will not be computed. The extent of missingness in these data, including by treatment and control arm, will be presented in the report. We will also run separate models for three components; 'internalising problems' (which combines the emotional symptoms and peer relationship problems scales, 10 items), 'externalising problems' (which combines the conduct problems and hyperactivity scales, 10 items) and the prosocial scale (5 items). This division of the scales has been shown to be more appropriate for low-risk or general population samples (Goodman et al., 2010).

Subgroup analyses

We will conduct separate analysis of the subgroup of pupils eligible for Free School Meals. Pupils eligible for FSM will be identified using the variable EVERFSM_6_P available from the NPD. This analysis will be conducted for both the primary and secondary outcome; all other subgroup and additional analyses will be conducted only for the primary outcome.

We will run analyses interacting treatment allocation with FSM status, as well as running separate models for the FSM and non-FSM subgroups. The same specification will be used as for the primary analysis. The effect size for FSM pupils will be presented on the basis of the subgroup model, as per the EEF statistical analysis guidance.

Given existing research has suggested differences in impact according to prior attainment (e.g. York and Loeb, 2018), as specified in the trial protocol, we will also conduct a separate subgroup analysis for "high" and "low" attaining pupils, based on the pre-test assessments. These groups will be defined by dividing the sample in half, based on the median score on the

⁴ Further details of the reasons for missingness will be presented in the evaluation report.

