A longitudinal follow-up analysis is beyond the scope of the current planned analysis. A longitudinal analysis could potentially be conducted in future to investigate whether any impact on longer-term outcomes is evident. Relevant outcomes for longitudinal analysis would be outcomes as measured in national assessments at KS1 (end Year 2) and KS2 (end of primary school). Any analysis of KS1 outcomes would need to be based on teacher assessments as schools are not required to submit information on test scores to DfE and thus only information on teacher assessments is available in the NPD. In addition, it could also be of interest to explore any impact on the phonics screening check usually undertaken at end Year 1. Any such analyses would be conducted according to the principles outlined in EEF Longitudinal Analyses Guidance.

Imbalance at baseline

We will report on the characteristics of the sample both at randomisation and at the point of analysis. This will include school characteristics (including Ofsted rating, school type (academy status), urban/rural location, number of pupils, percentage FSM pupils, percentage EAL pupils, percentage SEN pupils, and average school level performance at end Key Stage 2) and pupil characteristics (including age, gender, FSM eligibility, pre-test score).

We will present pupil characteristics on the basis of:

- all participating pupils as at the point of randomisation (regardless of whether in class selected for testing in schools with multiple classes).
- participating pupils at the point of randomisation in classes selected for testing
- pupils in the final analysis sample (that is, those with post-test YARC scores)

⁵ Please see the longitudinal analysis guidance.

Reporting will follow the standard EEF template, with means and standard deviations reported for continuous variables and counts and percentages in each category given for categorical variables. In line with EEF guidance, differences in pupil-level pre-tests (i.e. the YARC total score) will be reported as effect sizes. We will report the correlation between pre and post-test scores and compare these against the assumptions made in the sample size calculations. Histograms of pre and post-test scores will also be presented.

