We will assess balance by calculating absolute standardised differences (Imbens & Rubin, 2015) between the treatment and control groups and these will be presented in the report. Differences of greater than 10% will be considered as indicative of imbalance. If imbalance is observed we will run an additional sensitivity analysis incorporating any variables on which imbalance is present as additional covariates into the primary outcome model.

Missing data

We will report the number of complete cases (those without missing data). We will consider separately missingness in outcome data at post-test and missingness at pre-test, and will report the distribution of missing observations by treatment arm.

In the event of greater than 5% missing data at either cluster⁶ or individual level we will conduct further investigation into the mechanisms of missingness.

Any multiple imputation undertaken in response to missing data will focus on the primary analysis model, in line with EEF guidance. The extent to which multiple imputation is appropriate depends on the missingness mechanism.

Missing post-test data

If more than 5% of outcome data (total YARC post-test score) is missing (that is, as a percentage of the randomised sample) we will investigate the extent to which baseline characteristics (at school and pupil level)⁷ are correlated with missingness, using logistic regression, where the dependent variable is a binary indicator for missingness. If this shows significant associations with any of the characteristics, we would conduct an additional analysis including those covariates in the primary analysis model to assess the robustness of the main results.

Missing pre-test data

Again, where more than 5% of data is missing (that is, as a percentage of the randomised sample) we will undertake further investigation into the nature of missingness. This will follow the same approach outlined above of a logistic regression to explore the extent to which observed baseline characteristics are correlated with missingness.

Multiple imputation

Where the analysis above shows significant associations with the included characteristics, and where missingness does not depend on unobserved characteristics, the missing data are considered to be missing at random (MAR), and in this case, proceeding with multiple

⁶ That is, if data are missing for 5% of clusters.

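### YARC subscales already observed for a partly tested child are used neither in the primary model nor in imputing the missing total

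*SAP*

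**What the plan says.** - **Post-test score.** Under Primary outcome analysis, each of the four Early Reading subscales is standardised. They are then "added together to create a composite measure and re-standardised (calculated where all four components are non-missing").
- **Pre-test score.** The same section says: "The same approach will be adopted with the two subscales used for the pre-test". A pre-test total therefore needs both subscales.
- **Who is analysed.** Imbalance at baseline describes the last of its reporting groups as "pupils in the final analysis sample (that is, those with post-test YARC scores").
- **What counts as missing.** Missing post-test data works on the total alone: "If more than 5% of outcome data (total YARC post-test score) is missing", a logistic regression of missingness on baseline characteristics follows. The candidate predictors, in a footnote, are age in months, gender, free school meals status, pre-test score where available, and school.
- **Imputation.** Multiple imputation goes ahead if any significant association is found. The model uses the predictors that were significant, plus arm and school. It may cover both pre-test and post-test. Under Primary outcome analysis, missing pre-test scores in the main model are imputed on the same principles.
- **Subscales.** Additional analyses includes an exploratory model for each of the four post-test subscales.
- **Sample.** Sample size calculations overview says "the maximum available sample at post-test is 2,646". The version 1.1 update says "the decision was taken to stop post-testing in January 2021" and adds: "This has resulted in a smaller number of completed post-assessments (around a third of the anticipated number").

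**The concern.** For a child who completed three of four subscales, most of the primary outcome has been measured. Under these rules the total is missing, so the child leaves the primary model. If the total is then imputed, the strongest available predictors of it, namely the child's own other subscale scores from the same test, are not in the imputation model. Only baseline characteristics, arm and school can be. The same holds for a child with one of two pre-test subscales. That child needs an imputed covariate, and the observed half of the pre-test is not listed among its predictors.

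At stake is a modest amount of precision in a trial that has little to spare, and an imputed score that is poorer than the data allow. The plan also does not ask for partly tested children to be counted apart from untested ones. Most missing post-tests will be children never reached, so a single missingness figure would hide the partial records.

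**Working it through.** **1. Following one child through the rules.** Three of four subscales present:
- Total YARC: not calculated.
- Final analysis sample: excluded.
- Missing outcome: counted as missing.
- Imputation model: significant baseline predictors, arm and school; the three observed subscales are not listed.
- Exploratory subscale models: included for the three subscales completed.

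One of two pre-test subscales present: no pre-test total, so the covariate is imputed, again without the observed subscale.

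**2. How much three subscales say about four.** With four standardised subscales and a common inter-correlation r (not given in the SAP; 0.4 to 0.8 assumed),

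corr(sum of 3, sum of 4) = (3 + 9r) / √[(3 + 6r)(4 + 12r)]

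| r | correlation | variance kept |
|---|---|---|
| 0.4 | 6.6/√(5.4 × 8.8) = 0.957 | 92% |
| 0.6 | 8.4/√(6.6 × 11.2) = 0.977 | 95% |
| 0.8 | 10.2/√(7.8 × 13.6) = 0.990 | 98% |

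The unused information is therefore substantial for each such child. This holds when which subscale is missing does not depend on performance.

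**3. The plan's own detectable effect.** The SAP states 0.10 at 2,646 pupils. With two-sided 5%, 80% power, 40% of variance explained by the pre-test and 10% by school, the simple formula 2.80 × √[4(1 − 0.4)(1 − 0.1)/N] gives 0.080. Reading 0.4 as a correlation (R² = 0.16) gives 0.095 with the school term and 0.100 without it. The SAP does not state enough to settle which route was taken. Nothing here depends on it; the formula serves only to compare sample sizes.

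**4. Cost in precision.** A third of 2,646 is 882. The share of partial records is not given, so 2%, 5% and 10% are assumed. Interval widening is 1/√(1 − p) − 1.

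| p | children lost | N left | interval wider by | detectable effect, R² = 0.4 | R² = 0.16 |
|---|---|---|---|---|---|
| 0 | 0 | 882 | 0 | 0.139 | 0.164 |
| 2% | 18 | 864 | 1.0% | 0.140 | 0.166 |
| 5% | 44 | 838 | 2.6% | 0.142 | 0.168 |
| 10% | 88 | 794 | 5.4% | 0.146 | 0.173 |

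Both detectable-effect columns keep the 10% school term. Going from 2,646 to 882 raises the figure from 0.080 to 0.139 on the same formula. A further 5% of partial records adds 0.003.

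**5. Bias.** Simulations with a true effect of 0.10 removed 2% to 10% of children, with removal more likely at lower scores. The effect size was 0.096 to 0.101. In a sharper case, 5% were removed, all from the bottom fifth. The adjusted difference fell from 0.099 to 0.095 and the outcome SD from 1.00 to about 0.965, so the effect size was 0.095/0.965 = 0.098. Numerator and denominator shrink together.

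**6. Pre-test.** 2,392 of 2,646 pupils completed a pre-test, leaving 254 (9.6%). If completion means both subscales, any partial pre-tests lie among these 254. The SAP does not say how many there are.

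**The case against.** The strongest reply is that the all-four rule is explicit, pre-specified and consistent with the rest of the plan. No partial record is shown to exist, and the cost is small even if some do. The 882 are described as completed assessments, so subtracting partial records from them may count the loss twice. Totals missing by arm will be reported, missingness will be modelled, and completed subscales do reach the exploratory models. All of this stands. It is why the primary definition need not change, particularly as the composite would be redefined after post-testing had ended.

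Prediction from three subscales also has a weakness. If the missing subscale is the one the child finds hardest, the mean of the other three flatters that child. In a simulation (r = 0.6, bottom fifth, weakest subscale missing) the average score moved from −1.40 to −1.14 SD. This also stands, and it argues for using the mean of available subscales only as a sensitivity analysis.

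Four stronger readings are tempting, and the SAP does not support them:
- **That the YARC rule is stricter than the SDQ rule.** The SDQ tolerance is for items: up to two of a subscale's five may be absent, and its mean fills the gap. At subscale level the SDQ total also requires all four, exactly as the YARC does.
- **That the loss falls on the weakest readers.** The remarks on special educational needs and on floor effects both concern the pre-test, and a floor score is an observed score. Nothing is said about who has a partial post-test.
- **That the effect size is inflated.** Step 5 of the working shows that it is not.
- **That the rule caused the small sample.** Testing was stopped in January 2021 because of the third lockdown and the disruption to schools.

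None of these replies touches the imputation model, which leaves out the observed subscales without giving a reason.

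**Conclusion.** The point holds as a gap in how observed data are used. Subscales recorded for a partly tested child are unused in the primary model and absent from the stated imputation model, at both post-test and pre-test. It is not an error in the definition of the primary outcome.

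The size is modest: an interval about 1% to 5% wider if 2% to 10% of about 880 tested children are partial, and no material bias in the effect size. This rests on an assumed partial share, because the SAP gives none, and on a third of 2,646 as the tested number. If partial records prove rare, the gain is close to nil, and a count by arm would show that.

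**What to change.** Keep the all-four composite as the primary definition, and add the following to the SAP:

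1. Where multiple imputation is used, impute the missing subscales and then form and re-standardise the composite, or at least include the observed subscales as predictors of the total.
2. When only one of the two pre-test subscales is available, let it inform the pre-test covariate, as a predictor in the imputation.
3. Add a sensitivity analysis in which the post-test score is the mean of the available standardised subscales, re-standardised, when at least three of four are present.
4. Report by arm the number of children with one, two or three post-test subscales, and with one pre-test subscale, separately from those not tested.

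The cost is a paragraph of SAP wording and a little more analysis work. Three-subscale scores are slightly less reliable and can overstate a child who lacks the hardest subscale, so the sensitivity result should be read with that in mind and set beside the all-four result.
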